7.2. Background

In 2011, the EU Pharmacovigilance Working Party (PhVWP) recommended that the product information for domperidone-containing medicines should be updated to reflect the risk of adverse cardiac effects of domperidone including QT prolongation, arrhythmias, and sudden cardiac death, and that domperidone should be used with caution in patients with certain heart conditions, including heart failure, a previous heart attack, angina (chest pains), and heart rhythm disorders. In response to this recommendation, the SmPC was updated in 2012 to include QT prolongation as an adverse drug reaction (ADR).

In March 2013, the EMA PRAC initiated a review of domperidone-containing medicines at the request of the Federal Agency for Medicines and Health Products (FAMHP), under Article 31 of Directive 2001/83/EC over concerns about cardiac adverse effects of domperidone. Subsequently, PRAC recommended that the product label (Summary of Product Characteristics/SmPC and Patient Information Leaflet/PIL) of domperidone-containing medicines should be updated to strengthen the information regarding cardiac risks. In addition, PRAC raised concerns that there may be off-label use of domperidone for the stimulation of lactation in breastfeeding women, for the treatment of

gastro-oesophageal reflux disease (GERD), for the treatment of diabetic and non-diabetic gastroparesis, and for the treatment of symptoms of postural hypotension in Parkinson's patients. More recently the EMA asked that IBS be included in the present study as an off-label indication.

The recommended changes following conclusion of the Article 31 referral included the following:

- restriction of the indication to nausea and vomiting;
- limitation of duration of use to 7 days;
- reduction of the maximum daily dose to 10 mg TID for adults and adolescents (12 years of age and older and weighing 35 kg or more);
- reduction of the maximum daily dose to 0.25 mg/kg TID for neonates, infants, children (less than 12 years of age), and adolescents weighing less than 35 kg;
- contraindication of the combination with other drugs that increase the cardiac risks by themselves or increase the plasma level of domperidone; and
- contraindication in patients with moderate or severe hepatic impairment or certain cardiac conditions.

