9.3.2. Indication

Indication will be estimated from the diagnoses recorded in the time period preceding each domperidone prescription:

- The indication for the prescription will be defined as nausea/vomiting if the subject has a recorded diagnosis classified as nausea or as vomiting, on the day of the prescription or in the preceding 7 days.
- For those prescriptions whose indication is not defined as nausea/vomiting, the indication will be defined as off-label if the subject has, in the 2 months up to and

including the date of domperidone prescription, a diagnosis classified as one of the following:

- o GERD;
- Abdominal bloating, gastric dysmotility, delayed gastric emptying;
- o IBS;
- Suppressed lactation, failed lactation, lactation not established, decreased lactation, lactation problem; or
- Orthostatic hypotension and a diagnosis of Parkinson's disease.
- For those prescriptions not classified as above, the indication will be classified as unknown.

For a list of the diagnostic terms and codes that will be used to identify the above conditions, see Annex 6.

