9.7. Data Analysis

Data analysis in the study will be descriptive. Continuous variables will be presented using appropriate descriptive statistics, such as mean, median, standard deviation and range. Categorical variables will be presented using percent and frequency tables. The rates and 95% CI of all study endpoints (i.e., risk minimisation indicators) will be calculated for the 2011-2015 period, using quarterly time blocks for the pre- and post- risk minimisation implementation periods. The rates will be calculated per 1000 domperidone-treated patients or as percentage of domperidone prescriptions, as appropriate. Paediatric data will be described separately from adult patients and rate of paediatric use will be calculated as fraction of overall domperidone utilisation. Missing values will be reported as missing and no imputation will be undertaken. All data analysis will be done in SAS using the version that is current when the analyses are done.

The rates for the primary endpoints of the study (the proportion of all prescriptions that are consistent with the revised label) will be calculated 4 ways to address uncertainty about 1) Unknown indication (is it assumed to be nausea and vomiting and therefore on-label, or is it assumed to be some other indication and therefore off-label) and 2) Duration of use that may be shorter than the days' supply (prescriptions with more than 7 days' supply assumed to

be intended for ≤ 7 days use, and provision of additional tablets for possible future episodes, and therefore on-label, versus assumed to be for >7 days use and therefore off –label):

- 1. Unknown indication assumed to be nausea and vomiting. Duration assumed to be ≤ 7 days (most optimistic scenario) meets the following conditions:
 - a. Prescription for nausea and vomiting or unknown indication but no recent diagnosis of GERD, gastroparesis, IBS, symptoms of postural hypotension in Parkinson patients, or as an aid to lactation;
 - b. Dose no higher than recommended;
 - c. No prescription to patients with certain cardiac and hepatic conditions; and
 - d. No co-prescription with CYP3A4 inhibitors or QT-prolonging drugs. (This considers such contraindicated co-medications only when they were prescribed ≤ the date of the domperidone prescription.)
- 2. Unknown indication assumed to be an off-label indication, duration assumed to be \leq 7days (an intermediate scenario) meets the following conditions:

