 - Prescription for nausea and vomiting but no recent diagnosis of GERD, gastroparesis, IBS, symptoms of postural hypotension in Parkinson patients, or as an aid to lactation. Unknown indication will be assumed to be off-label (This differs from #1 above);
 - b. Dose no higher than recommended;
 - c. No prescription to patients with certain cardiac and hepatic conditions; and
 - d. No co-prescription with CYP3A4 inhibitors or QT-prolonging drugs (This considers such contraindicated co-medications only when they were prescribed ≤ the date of the domperidone prescription)
- 3. Unknown indication assumed to be nausea and vomiting, duration assumed to be the days' supply (an intermediate scenario) meets the following conditions:
 - Prescription for nausea and vomiting or for unknown indication but no recent diagnosis of GERD, gastroparesis, IBS, symptoms of postural hypotension in Parkinson patients, or as an aid to lactation (This is the same as in #1 above);
 - b. Duration (days' supply) ≤7 (This differs from #1 above and from #2 above, which don't examine days' supply)
 - c. Dose no higher than recommended;
 - d. No prescription to patients with certain cardiac and hepatic conditions; and

- e. No co-prescription with CYP3A4 inhibitors or QT-prolonging drugs. (Considers such contraindicated co-medications when prescribed ≤ the date of the domperidone prescription or prescribed within the days potentially covered by the domperidone prescription).
- 4. Unknown indication assumed to be an off-label indication, duration assumed to be the days' supply (most pessimistic scenario)
 - Prescription for nausea and vomiting but no recent diagnosis of GERD, gastroparesis, IBS, symptoms of postural hypotension in Parkinson patients or as an aid to lactation; Unknown indication assumed to be off-label (This differs from #1 above)
 - b. Duration (days' supply) ≤7 (This differs from #1 above and from #2 above, which don't examine days' supply.)
 - c. Dose no higher than recommended;
 - d. No prescription to patients with certain cardiac and hepatic conditions; and
 - e. No co-prescription with CYP3A4 inhibitors or QT-prolonging drugs. (Considers such contraindicated co-medications when prescribed ≤ the date of the domperidone prescription or prescribed within the days potentially covered by the domperidone prescription).

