9.9.2. Limitations

• The databases provide detailed information on prescribed and/or dispensed medications but not on the actual use of the medications by patients. This may

specifically be a limitation for drug that are used PRN, such as domperidone. Thus, patients may be classified as exposed when they are not actually taking the drug.

- The databases often do not record the intended duration of use of each prescription (days of supply). This can result in misclassification of drug exposure.
- Because domperidone is used as needed, missing information about the true length of treatment is likely to be an important source of uncertainty in estimating compliance with the recommendation to limit use to ≤7 days, and may also be an important source of uncertainty about the frequency with which domperidone is used concurrently with a contraindicated medication that was prescribed after domperidone was prescribed.
- In these databases prescriptions are not explicitly linked to diagnoses. The indication for which the drug is prescribed is deduced from the list of diagnoses documented in patient's records on or shortly before the day of the prescription. If a substantial proportion of prescriptions do not have a diagnosis that is plausible as an indication, this study is likely to leave appreciable uncertainty about the indications for which the medication is prescribed. Attempts to obtain this missing information from chart review or questionnaires would be subject to volunteer bias and there is no guarantee that the missing information on indication would be recorded in a high proportion of the charts that were made available.
- The databases do not include a unique patient identifier that would make it possible to identify as a single individual a patient who is attending multiple physicians. Therefore some diagnoses that contraindicate domperidone use, and some domperidone use that is concurrent with contraindicated medications, will be missed in this study.

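### The unknown-indication class merges 'no plausible diagnosis recorded' with 'another diagnosis recorded', so the four versions bracket each period's compliance but not the primary risk ratio

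*Protocol*

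**What the plan says.** Section 7.2 lists, among the recommended label changes, the "restriction of the indication to nausea and vomiting". Section 9.3.2 operationalises indication in three steps. A nausea or vomiting code on the prescription day or in the 7 days before makes the prescription on-label. Failing that, a diagnosis from a short list in the preceding 2 months makes it off-label. The list covers GERD; bloating, dysmotility or delayed emptying; IBS; lactation problems; and orthostatic hypotension with Parkinson's disease. Everything left over goes to one class: "For those prescriptions not classified as above, the indication will be classified as unknown".

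Section 9.7 then scores that class in four versions:

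- Version 1: "Unknown indication assumed to be nausea and vomiting. Duration assumed to be ≤ 7 days (most optimistic scenario").
- Version 2: "Unknown indication assumed to be an off-label indication, duration assumed to be" at most 7 days.
- Version 3: "Unknown indication assumed to be nausea and vomiting, duration assumed to be the days' supply (an intermediate scenario").
- Version 4: "Unknown indication assumed to be an off-label indication, duration assumed to be the days' supply (most pessimistic scenario").

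Section 8.1 makes the primary statistic, per country, the risk ratio of the compliant proportion between the two 1-year periods, reported for each version. Section 9.9.2 explains that prescriptions are not linked to diagnoses. It describes the resulting uncertainty in these terms: "If a substantial proportion of prescriptions do not have a diagnosis that is plausible as an indication".

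**The concern.** The limitation in Section 9.9.2 is about prescriptions with no plausible diagnosis. The rule in 9.3.2 is wider, because a prescription with a plausible but unlisted diagnosis is also called unknown. Annex 6 shows that this can happen. The codes shown there contain no dyspepsia or gastritis entry, and abdominal bloating, which 9.3.2 names as off-label, is mapped to a single code whose text is gastroparesis. On those codes, a dyspepsia or plain bloating diagnosis is unknown, passes the indication criterion in versions 1 and 3, and fails it in versions 2 and 4.

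At stake is how the four ratios are read. A reader will take the optimistic and pessimistic versions as enclosing the true change. They enclose the true level in each period. They need not enclose the ratio, because the make-up of the unknown class can change between periods. Changing why domperidone is prescribed is one purpose of the measure being evaluated.

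**Working it through.** The plan states no share for any indication class, so there is no figure of its own to reproduce. The check traces the rules and then applies them to assumed shares.

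**Set-up.** Split prescriptions into four classes:

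- *a*: nausea/vomiting coded
- *w*: unknown, truly nausea/vomiting
- *o*: unknown, truly another, unlisted use
- *L*: listed off-label diagnosis

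Let *c* be the share meeting the other criteria (dose, contraindications, co-medication; also days' supply in versions 3 and 4), taken as equal across classes and periods. From 9.3.2 and 9.7:

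- versions 1 and 3: c(a + w + o)
- versions 2 and 4: c·a
- truth: c(a + w)

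Versions 3 and 4 have their own *c*. A constant *c* cancels from a ratio, so version 3 behaves like version 1 and version 4 like version 2. Ratios below are post over pre, the direction used in Section 9.5.

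**Why the bracket fails for the ratio.** In each period, a ≤ a + w ≤ a + w + o, so the level is bounded. A move from *o* to *w* changes neither *a* nor a + w + o, so no version changes, although the truth does.

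**Illustration.** Assumed pre-period mix a/w/o/L = 20/30/20/30 (%): version 1 level 70, version 2 level 20, truth 50.

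| Post-period mix | Version 1 (and 3) | Version 2 (and 4) | Truth |
|---|---|---|---|
| A: 25/35/10/30 | 70/70 = 1.00 | 25/20 = 1.25 | 60/50 = 1.20 |
| B: 20/40/10/30 | 70/70 = 1.00 | 20/20 = 1.00 | 60/50 = 1.20 |
| C: 20/30/30/20 | 80/70 = 1.14 | 20/20 = 1.00 | 50/50 = 1.00 |
| D: unlisted use stops, other counts unchanged (20/30/0/30 out of 80) | 62.5/70 = 0.89 | 25/20 = 1.25 | 62.5/50 = 1.25 |

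With c = 0.8, case B reads 0.56 to 0.56 in version 1, 0.16 to 0.16 in version 2 and 0.40 to 0.48 in truth, with the same ratios.

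**Range over the size of the shift, same pre-period mix.**

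- *o* to *w* by 5, 10 or 20 points: truth 55/50 = 1.10, 60/50 = 1.20, 70/50 = 1.40; every version stays at 1.00.
- *L* to *o* by 5, 10 or 20 points: truth 1.00; versions 1 and 3 give 75/70 = 1.07, 80/70 = 1.14, 90/70 = 1.29.

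Section 9.5 treats a ratio of 1.1 as the smallest improvement of much public health interest, and most of these errors reach or exceed that.

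**What the per-period bounds allow in case B.** The level lies between 20 and 70 in both periods, so the ratio can lie anywhere from 20/70 = 0.29 to 70/20 = 3.50. The two reported ratios, both 1.00, give no hint of that width.

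**Effect of the split.** Score *o* as off-label in version 1 wherever another diagnosis is recorded, and assume no *w* prescription carries one.

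- All of *o* recorded: cases B, C and D give 60/50 = 1.20, 50/50 = 1.00 and 62.5/50 = 1.25, matching the truth.
- Half of *o* recorded (assumed): B gives 65/60 = 1.08, C gives 65/60 = 1.08 and D gives 62.5/60 = 1.04. Each is closer to the truth than version 1, but not equal to it.

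**The case against.** The strongest reply is that this is a declared bracket. Section 9.3.6 names unknown indication as an area of uncertainty and scores it both ways, 9.7 labels the extremes, and 8.1 reports a ratio for every version. The abstract lists only the version 1 rule but says further analyses address unknown indications that may be off-label. All of this stands for the level in each period. It does not answer the point about the ratio.

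Four stronger readings are tempting, and the documents do not support them.

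- *The indications removed by the restriction count as compliant.* The protocol never names the removed indications, and several gastrointestinal uses are already listed as off-label (Annex 6 codes heartburn and dysphagia under GERD). What can be shown concerns any unlisted use.
- *A fall in unlisted use cannot move the ratios.* Cases A and D show versions 2 and 4 can register it. In case D version 1 moves too, though in the wrong direction.
- *On-indication use is overstated by a stated number of points.* Any such figure multiplies two assumed shares (50% unknown and 20% of those with another diagnosis would give 10 points). It concerns indication alone: if 80% pass the other criteria, 10 points become 8 in the composite.
- *Such prescriptions should be off-label in all four versions.* Prescriptions are not linked to diagnoses, and an unlisted diagnosis may accompany uncoded nausea. Version 1 would then cease to be an optimistic bound.

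Sections 8.2 and 9.7 also plan a time trend and a tabulation of apparent indication. That helps, but as defined in 9.3.2 it keeps the two kinds of unknown together.

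**Conclusion.** The point holds in a limited form. The classification rule pools two kinds of prescription that the data can partly separate. As a result, the four versions bound compliance in each period without bounding the primary risk ratio. A shift within the unknown class is hidden from all four, and a shift from listed to unlisted diagnoses appears as improvement in versions 1 and 3.

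The size cannot be derived from the documents. The ratios above rest on an assumed mix, a constant share passing the other criteria, and listed and coded diagnoses being taken at face value. They show that an error of relevant size is possible, not that it will occur. Versions 2 and 4 and the disclosed limitation soften the problem without removing it. This is a worthwhile, inexpensive improvement and does not invalidate the design.

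**What to change.** In Section 9.3.2, split the remainder in two:

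- *Other plausible indication recorded*: no nausea/vomiting code in 7 days, no listed off-label diagnosis in 2 months, but a diagnosis from an upper-gastrointestinal code list, fixed before analysis, on the day or in the preceding 7 days.
- *No plausible diagnosis recorded*: the rest.

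Add the code list to Annex 6 in each coding system named in Annex 5. Tabulate both parts by quarter and by period. Keep the four versions in 9.7 as the declared bounds. In addition, report the version 1 and version 3 risk ratios with the other-recorded class scored as off-label, beside the ratios as now defined. State in 9.7 that the four versions bound the proportions and not the ratio.

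The cost is one more code list, one more class in the programs on data already extracted, and 2 extra ratios in each of 5 countries (2 × 5 = 10). The drawback is that a diagnosis recorded at or near the visit does not prove the reason for prescribing. The result should therefore stand as an added analysis and not replace the optimistic bound.

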9.3.3. Dose per Day

Dose per day will be described as dose in mg/day for subjects ≥ 12 years of age and in mg/kg/day for subjects < 12 years of age (if weight information is available for up to 1 year prior to the prescription). Exceeding the maximum daily dose of 30 mg for adults and 0.25 mg/kg TID for children will be evaluated.

9.3.4. Use in Patients with Contraindicated Conditions

The contraindication for moderate or severe hepatic impairment will be identified by any diagnosis of hepatic cirrhosis, hepatic failure, or hepatic coma, between 1 January 2011 and 1 day before the prescription was written. The cardiac contraindication will be identified by a diagnosis of QTc prolongation, ventricular arrhythmia, or congestive heart failure in the 6 months before the prescription was written, or a diagnosis of hypokalemia in the 30 days before the prescription was written.

9.3.5. Concurrent Use with Drugs that Prolong the QT Interval or are Potent CYP3A4 Inhibitors

Domperidone is used as needed, therefore the duration of use may not be the same as the number of days for which domperidone is supplied. As a result, duration of use will be assessed under the following 2 scenarios, which will be likely to bracket the actual (but unknown) situation:

- 1. Domperidone is used only for as little as 1 dose after it is prescribed, and
- 2. Domperidone is used for the entire number of days supplied.

For the first scenario, the assessment of concurrent use with contraindicated medications will focus on drugs that were prescribed before or on the date of the domperidone prescription and whose duration of use includes the date of the domperidone prescription. For the second

scenario, assessment of concurrent use with contraindicated medications will also include drugs that were prescribed during the days' supply of the domperidone prescription.

A list of drugs that are known to prolong the QT interval is provided in Annex 3 and those that are potent or strong CYP3A4 inhibitors appear in Annex 4.

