9.2. Setting and Study Population

9.2.1. Study Setting and Population

The study population will be defined as all patients receiving domperidone in the outpatient setting during the pre-defined periods (pre- and post- implementation periods of the risk minimisation activity) in the selected European Union countries (France, Germany, United Kingdom, Belgium, and Spain). Patients will be included in the study cohort if they have at least 1 prescription for domperidone in the selected databases during the pre-defined periods, and have membership or have been registered with the practice and have available medical history for at least 180 days before the domperidone prescription.

The date of the first prescription of domperidone in the pre-defined study periods will be defined as the index date. Patients will be followed from the index date to the earliest of the following dates:

- end of the study period;
- transfer out of the practice; or
- end of the practice's qualification as up to standard (a designation used in some databases to differentiate between practices that meet a data standard and those who do not for databases, such as CPRD).

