9.2.2. Study Period

The study period will be divided into a background period and pre- and post- implementation periods of risk minimisation measures as follows:

- A background period (1 January 2011 through 31 March 2013)
- A 1-year pre-implementation period of risk minimisation measures (1 April 2013 through 31 March 2014)
- A 1-year post-implementation period of risk minimisation measures (1 October 2014 through 30 September 2015)

The period during which the label change took place and the DHPC was sent will be used as the period during which the risk minimisation measures were implemented (1 April 2014 through 30 September 2014).

Because the amendments to the product information were suggested by the PhVWP in October 2011, the study will track prescribing pattern changes from 1 January 2011 (a time that preceded most of the discussion and implementation of the label changes, i.e., a background period) through 30 September 2015.

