Rates of the study endpoints will be assessed for the pre-implementation period (1 April2013 through 31 March2014) and will be compared with the 1-year post-implementation period (1 October2014 through 31 March2015). In addition, each of the above label requirements that contribute to the primary endpoint will be compared for the same two 1-year periods.

In addition:

- The apparent indications, and the days supplied (≤7 days vs. >7 days) will be tabulated.
- 2. There will be a table showing the demographic characteristics, of the study population (sex, age group).

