The LPD in Spain consists of anonymized patient records collected from patient management software used by GPs and select specialists (gastroenterology, cardiology, pneumology, rheumatology, gynecology, neurology, psychiatry, urology, endocrinology, internal medicine, ophthalmology, nephrology, trauma, pediatrics, and dermatology) during an office visit to document patients' clinical records from 2011 to the present (data collection from GPs began in 2011; data collection from specialists began in 2012) and is updated monthly. It includes patient demographics, comorbidities, diagnoses (by ICD-9-CM codes), symptoms, laboratory values, and prescriptions written (not dispensed).

LPD (Belgium)

The LPD in Belgium consists of anonymized patient records collected from patient management software used by GPs during an office visit to document patients' clinical records from 2005 to the present. Data are updated monthly and data for a study period are usually available within three weeks after the end of the study period. For example, for a study period ending December 2015, data are usually available by the end of January 2016. There are 370,000 active patients in the database. It includes patient demographics, comorbidities, diagnoses (by ICD-10 codes), symptoms, laboratory values, and prescriptions written (not dispensed).

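### The hepatic contraindication look-back starts on a fixed date, so post-period prescriptions are searched up to 1.5 years longer than pre-period ones

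*Protocol*

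**What the plan says.** Section 9.3.4 identifies moderate or severe hepatic impairment by a diagnosis of cirrhosis, hepatic failure or hepatic coma recorded "between 1 January 2011 and 1 day before the prescription was written". The same paragraph gives the cardiac conditions rolling windows: QTc prolongation, ventricular arrhythmia or "congestive heart failure in the 6 months before the prescription was written", and "a diagnosis of hypokalemia in the 30 days before the prescription was written".

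Section 9.2.2 sets the periods to be compared: "A 1-year pre-implementation period of risk minimisation measures (1 April 2013 through 31 March 2014") and "A 1-year post-implementation period of risk minimisation measures (1 October 2014 through 30 September 2015").

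The hepatic condition enters the results in three ways:
- Freedom from certain cardiac and hepatic conditions is required in all four versions of the composite (section 9.7). The ratio of compliant proportions between the two periods is the primary statistic in each country (section 8.1).
- Section 9.7 adds that "each of the above label requirements that contribute to the primary endpoint will be compared for the same two 1-year periods".
- Section 9.7 also asks for all endpoints in quarterly blocks over 2011-2015.

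Eligibility requires "available medical history for at least 180 days before the domperidone prescription" (section 9.2.1). The limitations in section 9.9.2 do not mention the look-back.

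**The concern.** A before/after comparison needs the same measuring rule in both periods. Here the start of the hepatic search is a calendar date and its end moves with the prescription, so every later prescription is searched for longer. A patient whose cirrhosis was last coded three years earlier is flagged in the post-period and missed through most of the pre-period, with no difference in what the prescriber did.

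The direction is known. Extra post-period flags make the contraindicated-conditions component look worse after the label change and the measures look slightly less effective. In the quarterly series the hepatic part starts from almost nothing in early 2011 and climbs as the window fills. A reader could take that climb for a real trend.

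**Working it through.** **1. Length of the search.** Look-back = prescription date minus 1 January 2011, with the periods of section 9.2.2. Means assume prescriptions spread evenly over each year.

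| Period | First day | Last day | Mean |
|---|---|---|---|
| Pre (1 Apr 2013 to 31 Mar 2014) | 821 days | 1,185 days | 1,003 days = 2.75 years |
| Post (1 Oct 2014 to 30 Sep 2015) | 1,369 days | 1,733 days | 1,551 days = 4.25 years |

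Gap: 1,551 − 1,003 = 548 days = 1.50 years. Ratio: 1,551 / 1,003 = 1.55. Section 9.7 gives a different post-period end, 31 March 2015. With that date the post mean is 1,459.5 days and the gap 456.5 days = 1.25 years, so the problem remains.

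These are maximum windows, for patients whose records reach back to 1 January 2011. In the first quarter of 2011 the window runs from 0 to 89 days.

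**2. Inflation of the hepatic flag rate.** The protocol gives no prevalence or recording frequency, so the inputs from here on are assumptions. Suppose prescribing is unchanged and existing liver disease is re-recorded at rate r per year. The chance that a window of w years contains a record is 1 − exp(−r·w). For r = 0.2 at the mean windows: 0.572 / 0.423 = 1.35. Averaged over the days of each period:

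| r per year | Post/pre inflation |
|---|---|
| 2.0 | 1.005 |
| 1.0 | 1.06 |
| 0.5 | 1.18 |
| 0.2 | 1.36 |
| Upper bound (detection proportional to window) | 1.55 |

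**3. Composite.** Let d be the pre-period proportion with a hepatic flag and k the inflation. If all else is compliant, or if hepatic flags are independent of the other requirements, the post/pre ratio of compliant proportions is (1 − k·d) / (1 − d). At the upper bound of k this gives 0.997 for d = 0.5%, 0.994 for 1% and 0.989 for 2%. At frequent re-recording it is 1.000 to three decimals.

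**4. Contraindicated-conditions component (cardiac and hepatic together).** Assume 1% hepatic flags in the pre-period, non-overlapping cardiac flags that are equal in both periods, and 22,000 independent prescriptions per period (the 2015 Belgian count in section 9.5, used for illustration). z = (p₂ − p₁) / √(2·p̄(1 − p̄)/n).

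With 3% cardiac and k = 1.55: p₁ = 4.00%, p₂ = 4.55%, z = 0.0055 / 0.00193 = 2.85. With k = 1.25: p₂ = 4.25%, z = 0.0025 / 0.00190 = 1.32.

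| Assumed cardiac flags | z at k = 1.25 | z at k = 1.55 |
|---|---|---|
| 1% | 1.82 | 3.87 |
| 3% | 1.32 | 2.85 |
| 5% | 1.09 | 2.38 |

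Repeat prescriptions to the same patient are correlated, because a flagged patient stays flagged. With an assumed design effect of 3, the 3% row falls to 1.32/√3 = 0.76 and 2.85/√3 = 1.65.

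**The case against.** The strongest reply concerns size. Cirrhosis persists, and if it is coded again at visits the longer window adds almost nothing: inflation is 1.06 at one recording a year and 1.005 at two. Only 180 days of history are required, so many patients may have a smaller realised gap than 548 days. The composite moves by about 1% at most, whereas the smallest ratio that section 9.5 treats as of interest is 1.1. The bias also runs against showing that the measures worked. All of this stands, and it limits the weight of the point. It does not make the windows equal: the 180-day rule is a floor, not a cap. Persistence of cirrhosis argues for a long window, not for one that differs between periods.

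A reader might infer that the study is bound to report a significant false worsening of hepatic contraindications. A hepatic-only comparison at 1% flagged would give z of 5.14 at inflation 1.55 and 2.49 at 1.25. The protocol does not set out that comparison: sections 8.1, 9.3.6 and 9.7 treat cardiac and hepatic conditions as one component, and the cardiac flags dilute the artefact. Those values also need an assumed 1% rate and independent prescriptions, and the larger one needs detection proportional to window length.

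A reader might also object that the search stops the day before the prescription, while the indication rule in section 9.3.2 includes that day. This applies equally to both periods and causes no pre/post bias.

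**Conclusion.** The point holds as a flaw in a rule that the protocol itself fixes. The hepatic search differs between the compared periods by up to 548 days (ratio 1.55), nothing in the protocol equalises it, and the direction is towards apparent worsening. The results most exposed are the contraindicated-conditions component and the early part of the quarterly series.

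The size cannot be determined from the protocol. Under assumed re-recording of 2 to 0.2 times a year the hepatic flag rate inflates by 1.005 to 1.36, with 1.55 as the upper bound, and the composite ratio shifts by about 0 to 1%. For the combined component, at 1% hepatic and 3% cardiac flags with 22,000 independent prescriptions per period, z is about 2.9 at inflation 1.55 and 1.3 at 1.25, and lower with repeat prescriptions. A spurious significant change in that component is therefore possible, not expected. The figures do not support inferring that the primary conclusion would be overturned. The change is worth making because it is cheap and removes a known difference in measurement.

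**What to change.** In section 9.3.4, replace the fixed start date with one rolling window of the same length before every prescription in both periods. It should be no longer than each database can supply for the pre-period. From 1 January 2011 that is at most 27 months (821 days to 1 April 2013). It is shorter for Spanish specialist records, since Annex 5 says "data collection from GPs began in 2011; data collection from specialists began in 2012": a start on 1 January 2012 leaves at most 15 months at 1 April 2013. Because only 180 days of history are required, even a window within these limits will not be fully observed for every patient.

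Add a 180-day version, which eligibility guarantees, as the strictly equal check on the pre/post comparison and as the definition for the quarterly series. It must not be cut off at 1 January 2011, or the first two quarters would still be short. Reporting the 180-day result for the annual periods as well lets the annual and quarterly figures be reconciled. Keep the search since 1 January 2011 as a sensitivity analysis.

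The cost is one sentence and a date filter. The downside is that some older hepatic diagnoses are no longer counted, so absolute hepatic prevalence is somewhat under-ascertained in both periods, most of all with 180 days.
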